10.5 Interim analysis

This has already been described in §8.7, p58.

10.6 Cost-Effectiveness Analysis (CEA)

General considerations:

This part of the study evaluates the potential efficiency of incorporating FDG-PET/CT in the diagnostic work-up versus usual practice in adult patients with FNAC-indeterminate thyroid nodules from a societal perspective. The economic evaluation is based on the general principles of a cost-effectiveness analysis and is performed alongside the randomised controlled clinical trial. Primary outcome measures for the economic evaluation, considering the 12 months follow-up period, are costs (direct and indirect) and quality adjusted life years (QALY). The incremental cost-effectiveness ratio (ICER) "cost per QALY gained" will be computed and uncertainty will be determined using the bootstrap method or Fieller method. A cost-effectiveness acceptability curve will be derived that is able to evaluate efficiency by using different thresholds (Willingness to Pay) for a QALY. The impact of uncertainty surrounding deterministic parameters (e.g. prices) on the ICER will be explored using one-way sensitivity analysis on the range of extremes. Secondary ICERs such as cost per unbeneficial patient management decrease will be presented and analysed as above. Furthermore, incremental Net Monetary Benefit (iNMB) will be computed based on a Willingness-to-Pay threshold of €80,000/QALY, as stated before.

Cost-analysis:

The cost-analysis exists of two main parts. First, on patient level, volumes of care will be measured prospectively using questionnaires filled-in by patients, completed by case record forms and patient files (supported by patient-based diaries). Per study-arm (experimental and control) full cost prices will be determined using activity-based costing (obviously) excluding the costs of the FDG-PET/CT in the control study arm. Cost items included are e.g.: surgical costs, costs of ¹³¹I-RIA, admission costs, costs for complications (secondary surgery, ICU etc.), out-patient clinic visits, use of relevant medications (calcium, vitamin D, 69iothyronine69, 69iothyronine etc.), blood tests ((para)thyroid function tests) and additional investigations (US, CT, biopsy, histopathology, etc.). Productivity losses for patients (sick leave) will be estimated using the iPCQ. The friction cost-method will be applied following the Dutch guidelines [68]. Also travel time to an out-patient clinic and related expenses will be considered using the iMCQ. The second part of the cost-analysis consists of determining the cost prices for each volume of consumption in order to use these for multiplying the volumes registered for each participating patient. The Dutch guidelines for cost-analysis will be used [68]. For units of care/resources where no guideline of standard prices is available, real cost prices will be determined.

Patient outcome analysis:

The effect analysis adheres to the design of a randomised controlled trial and measures at baseline (T0) and after surgery+¹³¹I-RIA/2 months, 6 months and 12 months (T1-3) follow-up. To measure the quality of the health status of the patients, a validated HRQoL instrument will be used: the EQ-5D-5L. This HRQoL instrument will be completed by the patients and is available in a validated Dutch translation [70]. The EQ-5D-5L is a generic HRQoL instrument comprising five domains: mobility self-care, usual activities, pain/discomfort and anxiety/depression. The EQ-5D-5L index is obtained by applying predetermined weights to five domains. This index gives a societal-based global quantification of the patients' health status on a scale ranging from 0 (death) to 1 (perfect health). Patients will also be asked to rate their overall HRQoL on a visual analogue scale (EQ-5D-VAS) consisting of a vertical line ranging from 0 (worst imaginable health status) to 100 (best imaginable).

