8.3 Study procedures

8.3.1 FDG-PET/CT of head and neck

A single FDG-PET/CT of the head and neck without a contrast-enhanced CT is performed in all patients in the local centre according to the EANM guidelines [50], independent of allocation results. The scanned area ranges from meatus acusticus externus to the fossa jugularis sternalis (or down to the lower margin of the arcus aortae in case of retrosternal goitre), with arms down and preferably using a head rest (Figure 3, p49). Only a section of the body is scanned as the possibility that a single (PET-positive) lesion outside the thyroid bed is the only evidence of DTC is extremely rare and decreasing the scan range will decrease the effective dose of the investigation. Most of these findings are supposed to be coincidental findings unrelated to DTC and harbour a very low a posterior probability to be of serious consequences. could be considered as "screening a healthy population using FDG-PET" which is highly controversial and probably will lead to increase use of diagnostics and expenditure of public funds and could demotivate physicians in including patients in such a trial. E.g. findings of a positive lesion in the colon would certainly be unrelated to DTC, might lead to endoscopic examination which are costly, could lead to complications for the patient, have a low probability to lead to a serious medical condition requiring therapy and would finally demotivate the physician to include more patients.

[figure not shown]

Figure 3: Position of the normal thyroid.

As an example guideline, in short: patients are asked to refrain from eating and drinking for 6 hours, only water and medications are allowed. In insulin-dependent diabetics, insulin levels should be as low as possible, while maintaining normoglycemia (serum fasting glucose <200 mg/dL [<11.1 mmol/L]). No (short-acting) insulin may be injected in the 4 hours before FDG-infusion to reach normoglycemia.

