FDG-PET/CT is an established (and for a number of other indications proven cost-effective) procedure for multiple oncological and non-oncological issues, covered by the Basic Insurance Package. FDG-PET/CT is a relative non-invasive procedure with only minimal risks attached to it (see §13.1.1: FDG-PET/CT, p78). Administration of FDG does not result in any adverse events. An FDG-PET/CT scan is widely available in almost all hospitals in the Netherlands and can usually be performed within 3 working days. A standard operating procedure (SOP) will be available.

The use of different acquisition protocols (for different departments and different PETscanners) causes heterogeneity in image quality. This probably deteriorates the power of this study, but at the same time will improve applicability of the results for clinical practice. The central PET-reading committee of this study has experience with multiple models of PETscanners.

[figure not shown]

Figure 4: Topograms showing the major landmarks: the meatus acusticus externus (*MAE*), the fossa jugularis sternalis (*FJS*) and the lower margin of the arcus aortae (*LAA*).

Definition of positive and negative FDG-PET/CT:

A positive FDG-PET/CT is defined as focal FDG-accumulation at the site of the FNACindeterminate thyroid nodule higher than (thyroid) background. All other cases are considered FDG-PET/CT negative. For example, see Figure 5, p51. In case of diffuse thyroid FDG-uptake (thyroiditis), the same definition is used, but the higher background should be noted.

The treating physician should receive written notification of the consequences of this result (surgery or not) within one week of the FDG-PET/CT. No disclosure of PET-result of the thyroid nodule (positive or negative) or the study arm allocation should be given.

Contralateral incidentalomas:

In case of an extra FDG-PET/CT-positive thyroid lesion *contralateral* to the thyroid nodule under investigation, it is considered an incidentaloma and worked-up accordingly (~35% harbour malignancy [56]) before a *ipsilateral* hemithyroidectomy is performed. This is not necessary in case total thyroidectomy is scheduled.

Relevant coincidental findings:

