In case of clinically relevant coincidental findings (e.g. suspicion of a head & neck carcinoma, oesophageal carcinoma, lung carcinoma or (FDG-avid) cervical or mediastinal lymphadenopathy) this should be reported to the treating physician in writing. Cervical lymphadenopathy without focal thyroid uptake needs further work-up (e.g. US+FNAC, MRI).

[figure not shown]

Figure 5: Example of a FDG-PET/CT positive thyroid nodule in the isthmus, which proved to be a 10 mm differentiated papillary thyroid carcinoma (pT1a cN0M0)

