The reason for this is that it was not the FDG-PET/CT-scan that proved the indication for diagnostic surgery, as the lesion under investigation was considered negative, even though the patient is diagnosed correctly with DTC at surgery. In other words: if the patient would have been included in the experimental study arm, the false-negative lesion would have led to a follow-up policy and the contralateral malignancy would never have been diagnosed by a hemithyroidectomy of the site of the false-positive lesion (unless the work-up for a contralateral incidentaloma would have let to a true-positive result).

As stated before, PET-incidentalomas must be worked-up before surgery unless total thyroidectomy is planned as the initial procedure. Abovementioned rare case could therefore only occur if the contralateral PET-incidentaloma was found benign/unsuspicious at work-up or initial total thyroidectomy was planned.

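### The control-arm costing rule names only the PET/CT for exclusion, so care prompted by the study scan stays in a comparator meant to represent practice without PET and understates the incremental cost of PET

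*Protocol*

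**What the plan says.** - **Comparator.** Protocol §10.6 (general considerations) says that this part of the study "evaluates the potential efficiency of incorporating FDG-PET/CT in the diagnostic work-up versus usual practice". Usual practice involves no PET.
- **Who is scanned.** Under §8.3.1 the scan "is performed in all patients in the local centre according to the EANM guidelines [50], independent of allocation results".
- **What happens to findings.** For an additional PET-positive lesion in the other thyroid lobe, §8.3.1 states that "it is considered an incidentaloma and worked-up accordingly". Other relevant coincidental findings go to the treating physician in writing, and "Cervical lymphadenopathy without focal thyroid uptake needs further work-up (e.g. US+FNAC, MRI". None of this is limited to one arm. §8.3.4, in the multifocality rule whose worked example is a control-arm patient, repeats that "PET-incidentalomas must be worked-up before surgery unless total thyroidectomy is planned as the initial procedure".
- **What is costed.** §10.6 (cost-analysis) determines full cost prices per arm, "excluding the costs of the FDG-PET/CT in the control study arm". The items listed include out-patient visits, secondary surgery and "additional investigations (US, CT, biopsy, histopathology, etc". Sick leave and travel are also counted. Nothing is said about care set off by the control-arm scan.
- **What is recorded.** §8.1.2 has as a secondary endpoint the fraction of extra diagnostics caused by coincidental PET findings. §8.1.3 has investigations for such findings retrieved from patient files.

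**The concern.** The control arm stands in for practice without PET, and taking the scan price out of it shows that the sponsor intends this. The same reasoning covers any test, visit or procedure that happened only because the study scan showed something. If that care stays in the control arm, the comparator is too expensive.

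Randomisation makes the expected frequency of such findings equal in the two arms. Leaving their cost in both therefore tends to cancel it out of the difference, and a cost that a hospital adopting PET would really bear drops out of the evaluation. This error is systematic, so more patients would not reduce it. The planned one-way sensitivity analysis varies deterministic inputs such as prices and would not expose it.

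**Working it through.** **Inputs from the protocol**
- Modelled five-year mean cost: EUR 8,804 (current practice) and EUR 7,983 (with PET), §1.4.1.
- Stated saving EUR 822, gain 0.036 QALY, iNMB EUR 3,684, §1.4.3; willingness to pay EUR 80,000 per QALY, §1.4 and §10.6.
- Unit costs: hemithyroidectomy EUR 4,419, total thyroidectomy EUR 6,238, completion thyroidectomy EUR 6,618, radioiodine ablation EUR 2,479, §1.4.1.
- Control arm: 44 patients, §4.4.

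**Reproducing the plan's figures**
- Saving: 8,804 − 7,983 = EUR 821, against 822 stated (rounding).
- iNMB: 822 + 80,000 × 0.036 = EUR 3,702, against 3,684 stated (within 0.5%, consistent with rounding of the QALYs).

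**Size of the bias from work-up.** Let r be the share of control patients with PET-prompted work-up and c its mean cost. Mean control cost is too high by r × c, whatever the experimental arm incurs. The protocol gives neither r nor c. I assume r = 2-10% and c = EUR 500-2,000.
- Low end: 0.02 × 500 = EUR 10 per control patient.
- High end: 0.10 × 2,000 = EUR 200 per control patient.
- Against the modelled saving: 10/822 = 1.2%; 200/822 = 24.3%.
- Against the modelled iNMB: 10/3,684 = 0.3%; 200/3,684 = 5.4%.

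Both yardsticks are five-year model results and the trial analysis covers 12 months, so the percentages only indicate scale. At EUR 2,000 per work-up, r would have to reach 822/2,000 = 41% to offset the whole modelled saving.

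**Size of the bias from a change of operation.** Control patients are already scheduled for thyroid surgery (§5.1), so the relevant quantity is the increment.
- Hemithyroidectomy to total thyroidectomy in one patient: 6,238 − 4,419 = EUR 1,819; 1,819/44 = EUR 41 per control patient.
- The same with radioiodine: 1,819 + 2,479 = EUR 4,298; 4,298/44 = EUR 98 per control patient.
- Opposite direction: if the patient would otherwise have had hemithyroidectomy followed by completion (4,419 + 6,618 = EUR 11,037), starting with total thyroidectomy costs 11,037 − 6,238 = EUR 4,799 less.

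The sign is therefore clear for added tests and visits, and less so for surgery that follows from them.

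**The case against.** **The protocol does not say that PET-prompted care is kept in the control arm.** That is correct. The exclusion clause signals an intention to cost that arm as care without PET, the cost list is illustrative, and a SAP that is not shown might settle attribution. A reader should not infer that the sponsor chose to charge this care to the comparator. What stands is that §10.6 states a costing rule, asks for full cost prices and names one exclusion. An analyst following it would leave the downstream care in. Reading the costs of the scan to include everything that follows from it is possible, but nothing in the text supports it.

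**The size is assumed and may be small.** This stands too. The scan range is restricted partly to limit incidental findings (§8.3.1, §11.4), and no case in the assumed range offsets the modelled saving.

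**One PET-prompted operation might seem to add a full EUR 4,419, or about EUR 100 per control patient.** The documents do not support that as a minimum. A change of operation in a patient already awaiting surgery adds EUR 41 per control patient, or EUR 98 with radioiodine, and can even lower cost.

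**The iNMB might seem certain to be biased towards PET.** This is not established. The same work-up may change control-arm QALYs in a direction that the protocol does not determine. At EUR 80,000 per QALY, EUR 200 is offset by 200/80,000 = 0.0025 QALY.

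**Conclusion.** The point holds for the incremental cost. The control arm represents practice without PET, yet the written rule leaves in it the cost of care that exists only because of the study scan. For tests and visits, this understates the incremental cost of PET. The ICER and iNMB inherit the error on the cost side; their net direction is open because QALYs may shift as well.

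The size cannot be derived from the protocol. It is EUR 10-200 per control patient if 2-10% have PET-prompted work-up at EUR 500-2,000 each, and it changes in proportion to either assumption. The documents do not support a claim that the economic conclusion would reverse. The matter deserves correction because the error is systematic, concerns a cost that the comparison is meant to capture, and is cheap to remove.

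**What to change.** Add to §10.6 that, in the base case, resource use attributable to reported study-PET findings is excluded from control-arm costs together with the scan, and is kept in the experimental arm. Say that this covers thyroid incidentalomas and non-thyroidal findings alike, and that it includes tests, visits, resulting procedures and sick leave.

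Flag these items from what §8.1.2 and §8.1.3 already record. SO1e alone is not enough, because it is confined to non-thyroidal findings and would miss contralateral thyroid lesions.

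Add a sensitivity analysis with these volumes left in both arms. State that control-arm QALYs may still carry effects of the work-up, so costs and effects in that arm will not describe exactly the same pathway.

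The cost is a short addition to §10.6, an attribution flag (on investigations already recorded, and also on the visits, procedures and sick leave that followed) and one extra analysis. Some judgement is needed on which care the scan prompted, particularly for later surgery and sick leave; the attribution criteria should be set before costs are compared by arm. No study procedure or sample size changes.

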11. ETHICAL CONSIDERATIONS

11.1 Regulation statement

This study will be conducted according to the principles of the Declaration of Helsinki (version of the 59th WMA General Assembly, Seoul, October 2008) and in accordance with the Medical Research Involving Human Subjects Act (WMO), the European Union (EU) General Data Protection Regulation (GDPR), the National Thyroid Cancer guideline [5] and the local (hospital) guidelines.

11.2 Recruitment and consent

Clinicians (especially endocrinologists) of participating hospitals will check in- and exclusion criteria when they have a patient with indeterminate FNAC for a thyroid nodule. They will inform the patient on the study. Patient will be permitted at least 48 hours of time to consider their decision and will be given the opportunity to discuss remaining questions about study participation with their treating physician. After this, written informed consent will be obtained. At the request of the patient, we will permit the informed consent procedure to take place through mail or email. Once written informed consent has been obtained, cytological material will be sent for central revision and thereafter patients are registered centrally.

The treating physician will hear whether the patient can be entered in the study, i.e. all inclusion criteria are met and all exclusion criteria are excluded (preferably within 2 working days from registration).

Once the patient is randomised (and has a study ID), an FDG-PET/CT of the head and neck can be planned, preferably by the treating clinical physician. The coordinating investigator will inform the department of nuclear medicine of the participating hospital on the acquisition protocol and will assure no report will follow. The images will be sent to the coordinating investigator who will review them and will inform the treating physician whether or not surgery is deemed unnecessary (§8.3.1, p48) and a confirmatory US should be planned (§8.3.2, p52). This feedback will take place within one week after the FDG-PET/CT has taken place. For the patient information letter and informed consent form see Appendix IX: Patient information Letter, declaration of insurance, informed consent and travelling expenses declaration form (in Dutch), §15.7, p98.

11.3 Objection by minors or incapacitated subjects

Minors are not included (§4.2, p36) and incapacitated adults are excluded from this study (§4.3, p37). Thyroid nodules and DTC are rare in children.

11.4 Benefits and risks assessment, group relatedness

The benefits for the individual patient is that he or she as a 2/3 probability to be included in the experimental arm in which only ~60-65% will be operated upon (instead of ~100% in the control study-arm, which is considered standard care). By lowering the amount of unnecessary invasive procedures also the number of complications and side effects are lowered.

As described elsewhere in detail (§13, p78), the risk for the individual patients are mainly based on delayed treatment for the indolent growing DTC in case of a false-negative PET-scan in the experimental study arm and the risks attached to the use of ionising radiation and of incidental PET findings.

The risks of consequences of delayed treatment for DTC are minimised by using a confirmatory US in the individual patient (§8.3.2, p52) and by performing interim- (§8.7, p58) and posthoc (§8.4.1, 56) analyses on the control study arm (in which both FDG-PET/CT and final histology is obtained).

The risk of ionising radiation (§15.6, p97) is minimised by several means: using (ultra) lowdose CT, minimising the scan range, thus minimising the amount if tissue exposed to (ultra) low-dose CT radiation and exclusion of minors that would both have increased effective dose per amount of FDG and suffer more detriment per unit of effective dose. By decreasing the scan range, the scan time is also limited, encouraging nuclear medicine departments to scan at a decreased speed (e.g. 4 min per bedposition or longer) by which means they can lower the administered FDG-dose.

The risks of additional (invasive) diagnostic procedures for incidental PET-findings is minimised by only scanning head, neck and thoracic inlet.

The burden to the patients consist of a single FDG-PET/CT (1.5h, in all patients, §8.3.1, p48), a single confirmatory US (0.5 h, in ~35-40% of the experimental arm or approximately ~25% of all patients included, §8.3.2, p52) and 4 times 6 questionnaires (120-160 min, in all patients, §8.3.3, p52). On average these 3 types of investigation therefore take in total 4-4.5 h per patient.

Travel expenses of included patients to and from the hospital will be compensated for the FDG-PET/CT and the confirmatory US (\in 0.19/km or comparable and possible additional costs for parking at the hospital, according to the locally set reimbursement rates and in consultation with the project leaders).

11.5 Compensation for injury

The sponsor/investigator has a liability insurance which is in accordance with article 7, subsection 9 of the WMO.

The sponsor (also) has an insurance which is in accordance with the legal requirements in the Netherlands (Article 7 WMO and the Measure regarding Compulsory Insurance for Clinical Research in Humans of 23th June 2003). This insurance provides cover for damage to research subjects through injury or death caused by the study.

€ 450.000,-- (i.e. four hundred and fifty thousand Euro) for death or injury for each subject who participates in the Research;

€ 3.500.000,-- (i.e. three million five hundred thousand Euro) for death or injury for all subjects who participate in the Research;

€ 5.000.000,-- (i.e. five million Euro) for the total damage incurred by the organisation for all damage disclosed by scientific research for the Sponsor as 'verrichter' in the meaning of said Act in each year of insurance coverage.

The insurance applies to the damage that becomes apparent during the study or within 4 years after the end of the study.

11.6 Incentives

Travel expenses of the included patients to and from the hospital will be compensated for the FDG-PET/CT and the confirmatory US (≤ 0.19 /km or comparable and possible additional costs for parking at the hospital, according to the locally set reimbursement rates and in consultation with the project leaders).

